6. SAFETY ASSESSMENT

6.1. Adverse Event Assessment and Reporting

Comprehensive assessments of any apparent adverse event(s) (AE) experienced by the study subject will be performed throughout the course of the study.

The PI will submit reports of unexpected Serious adverse events (SAEs) and other unanticipated problems to the Institutional Review Board (IRB) at Boston Children's Hospital and to OpenBiome according to their policies.

The PI will report events that are both serious and unexpected and that are associated with FMT/study intervention to the FDA and other applicable health authorities within the required timelines as specified in 21 CFR 312.32 (IND Safety Reports).

The following unexpected AEs will be assessed, recorded and reported to the Data Safety Monitoring Board (DSMB) on an expedited basis: all SAEs, AEs grade 3 (according to CTCAE 5.0 (31) if applicable) or above, and any unexpected AEs grade 2 or above that is possibly or probably related to FMT (as determined by a blinded investigator). Only an AE that meets the above criteria will be recorded and reported. Each reported AE will be described by its duration (i.e., start and end dates), regulatory seriousness criteria if applicable, expectedness, suspected relationship to the study treatment, and actions taken (a blinded investigator will determine expectedness, severity and relationship to study treatment).

Individual subject participation will be temporarily halted until the DSMB determines appropriateness of re-initiation of therapy in any subject experiencing an adverse event resulting in: an Emergency Department visit that is possibly or probably related to FMT, significant worsening of their disease, or experiences 1 SAE Grade \geq 3.

Individual subject participation in the study will be permanently stopped if a SAE Grade ≥ 3 is deemed possibly or probably related to FMT, including any hospital admission.

If 2 or more subjects experience 1 SAE grade \geq 4, all study activities will be halted until the DSMB determines appropriateness of re-initiation of therapy in any subject.

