4.1.5. Drug Related Risks

Theoretically, there is a small potential of transmission of an unknown pathogen when delivering human donor fecal material to a recipient. Additionally, there is potential concern that the recipient might have an allergic reaction to a food component in donor stool that they might not be aware of and the donor has not avoided. There is also a potential that certain disease states might be inherently related to the gut microbial environment and a donor's risk for disease might be transmitted to a recipient. These risks will be mitigated by carefully screening donors for health status as well as relevant (known) infectious pathogens.

The literature to date comprises 100's of cases of FMT for CDI as well as for IBD. To date, no serious adverse events have been reported. Both Vermeire and Vandenplas reported systemic symptoms of fevers and abdominal pain in refractory IBD patients after FMT that resolved within 24-48 hours without intervention. (10,14) Pierog at Columbia University reported the development of granulomatous appendicitis two weeks after FMT for the indication of recurrent CDI in a pediatric patient with underlying ileocecal granulomatous Crohn's disease, but there is no clear reason to assume FMT is responsible for this otherwise Crohn's related outcome. (23) Quera reported a repeated sepsis episode with multi-drug resistant E. coli in a 61 year old male ill Crohn's patient treated by FMT for recurrent CDI who had had several episodes of similar bacteremia previous to FMT. (24) [name] reported a case of a 37 year old man who self-administered FMT at home for his ulcerative colitis who subsequently developed CMV colitis. (25) Additionally, De Leon reported a case of a patient who experienced a transient flare of ulcerative colitis that had been quiescent for twenty years after FMT for recurrent CDI. (26)

Retention enema is likely low-risk but may be less effective in some patients with inability to retain the FMT inoculum or placebo rectally. Mild discomfort and distress with anal manipulation are possible, though enemas are routinely used in our clinical practice to treat distal IBD colitis as well as constipation. Indeed in adult populations with advanced age, multiple comorbidities or limited life expectancy, this delivery mode is preferable. (27)

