5.3.3. Clinical Outcomes

Primary Outcome Measures

- 1. Presence of FMT-related adverse events grade 2 or above.
- 2. Proportion of subjects with any FMT-related adverse events of grade 2 or above at 8 weeks post-FMT. Patient related outcomes of rectal bleeding and number of bowel movements. Rectal bleeding will be assessed using common language from PUCAI scoring. (See Figure 1)

Figure 1.

Rectal Bleeding
None
Small amount only, in less than 50% of stools
Small amount with most stools
Large amount (> 50% of stool content)

Secondary Outcome Measures

- 1. Remission as defined by PUCAI of ≤ 9
- 2. Improvement in inflammatory biomarkers (stool calprotectin, serum ESR/CRP, albumin, Hematocrit).
- 3. Changes in gut microbial composition.
- 4. Improvement of PUCAI of \geq 20 points. (30)
- 5. Assessment of engraftment of donor microbes into recipients.

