7. STATISTICAL CONSIDERATIONS

7.1. Power Calculation

The primary aim of this phase I/II study is to establish whether or not FMT is a safe treatment for children and young adults with UC. Based on clinical experience, adverse events (AEs) in IBD patients are common and include abdominal pain, cramping, diarrhea, fever, bloody stool, vomiting, frequent defecation, joint pain, and eye pain. It's estimated that 70% of patients in any given year will experience a flare of their disease and have some or a combination of these symptoms. Safety, therefore, needs to be assessed relative to the high prevalence of AEs in this population. For the primary outcome, we will take any new reported SAEs or worsening of the existing AEs during the study period following enrollment into account.

The study will be powered for equivalence in the proportion of new SAEs or worsening of the existing AEs, assuming null (Ho) and alternative (Ha) hypotheses defined as follows:

$$\begin{split} & \text{Ho: } p1-p2 \leq \text{-}\delta_L \ \text{ or } p1-p2 \geq \delta_U. \\ & \text{Ha: } \delta_L \leq p1-p2 \leq \delta_U \end{split}$$

where p1 is the proportion of new SAEs or worsening of the existing AEs in the placebo group, p2 is the proportion in the FMT group, δ_L is the lower margin and δ_U is the upper margin. We expect to enroll a total of 60 patients into this study for a total of 30 FMT and 30 placebo patients. Assuming the rate of new incident SAEs or worsening of existing AEs in the placebo group is 10%, there will be 82% power to reject Ho that the difference in proportions is 0.20 or greater from zero in the same direction. Similarly, we will have an 85% power to reject a difference of 0.25 or greater if the rate of new incident SAEs or worsening of existing AEs increases to 15%.

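### Section 6.1 restricts which adverse events are recorded, not only which go to the DSMB, so events that the primary safety outcomes count can go uncaptured

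*Combined protocol and SAP*

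**What the plan says.** Section 6.1 opens by promising full assessment of any apparent AE throughout the study. It then introduces a list: "The following unexpected AEs will be assessed, recorded and reported to the Data Safety Monitoring Board (DSMB) on an expedited basis". The list has three items: all SAEs, AEs of CTCAE grade 3 or above, and "any unexpected AEs grade 2 or above that is possibly or probably related to FMT". The next sentence is "Only an AE that meets the above criteria will be recorded and reported". The attributes (dates, seriousness, expectedness, relationship, action taken) are then requested only for events that pass the filter: "Each reported AE will be described by its duration".

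The outcomes are defined elsewhere. The first primary outcome in section 5.3.3 is "Presence of FMT-related adverse events grade 2 or above", and the second is the proportion of subjects with such an event at 8 weeks. Neither carries a condition on expectedness. For its primary outcome, section 7.1 takes "any new reported SAEs or worsening of the existing AEs during the study period following enrollment into account". Section 7.3 compares the arms on new SAEs or an upgrade of existing AEs. Neither section limits worsening by grade, relatedness or expectedness.

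Section 8 describes a running log of symptoms, medication and adverse events, collected on case report forms and entered in the database. It states no filter.

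**The concern.** Safety is the primary aim, so what reaches the database determines the primary result. The 6.1 sentence uses the verb for recording as well as the one for reporting. If site staff follow it, some events that the primary outcomes count never reach the analysis, and they cannot be reliably recovered afterwards.

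The filter can plausibly reach relevant events. Section 7.1 says that "adverse events (AEs) in IBD patients are common and include abdominal pain, cramping, diarrhea, fever" and other symptoms, and section 4.1.5 describes publications that "reported systemic symptoms of fevers and abdominal pain in refractory IBD patients after FMT". An investigator could class such events as expected. This is an inference, because the documents do not define expectedness.

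Oversight may be affected too. Section 6.2 has the DSMB review adverse events as described earlier in the protocol. Section 3.2.1 has the DSMB judge safety in the first 10 subjects before enrolment widens. If *described earlier* means the 6.1 list, that judgement rests on filtered data.

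**Working it through.** **Step 1. Each type of event against each rule.** The last column reads the 6.1 sentence literally.

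| Event | Counted in 5.3.3 | Counted in 7.1/7.3 | Recorded under 6.1 |
|---|---|---|---|
| Non-serious grade 2, FMT-related, unexpected | Yes | If it worsens an existing AE | Yes |
| Non-serious grade 2, FMT-related, expected | Yes | If it worsens an existing AE | **No** |
| Existing AE going from grade 1 to 2, non-serious, judged unrelated | No | Yes | **No** |
| New SAE, expected | If related and grade 2 or above | Yes | Depends on the lead-in |
| Non-serious grade 3 or above, expected | If related | If it worsens an existing AE | Depends on the lead-in |

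The two **No** rows hold on any reading of the list. The last two rows turn on whether *unexpected* in the lead-in governs all three items or only the third, where it is repeated. If it governs all three, expected SAEs and expected grade 3 or above AEs are lost as well.

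**Step 2. If section 8 governs instead.** No events are lost. But section 8 does not ask for grade, expectedness or relatedness, and 6.1 asks for them only for reported events. Section 5.3.3 needs grade and relatedness. The upgrade in 7.3 needs a starting grade. AEs are assessed at Day -8 (section 5.1) and symptom logs are taken at study entry (section 5.2.1), but no section asks for a baseline CTCAE grade.

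**Step 3. The plan's own power figures, for context.** With equal true rates p, n = 30 per arm and margin m, the power of a single one-sided test is Φ(m/SE − 1.645), where SE = √(2p(1−p)/30).

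- p = 0.10, m = 0.20: SE = 0.0775, power 0.826 (plan: 82%).
- p = 0.15, m = 0.25: SE = 0.0922, power 0.857 (plan: 85%).

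The plan's inputs are therefore used below. This point does not dispute the power figures.

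**Step 4. What lost events could do to the 7.3 test.** Let d be the observed difference in proportions. Equivalence is declared when (m − d)/SE and (m + d)/SE both exceed 1.645. The plan names no variance method, so two are shown: Wald (observed proportions) and score (proportions estimated under the margin constraint). Binomial probabilities are summed over all pairs of counts from 0 to 30. The true FMT rate is set worse by the full margin, so declaring equivalence is an error. The losses are assumptions, applied to the proportion of subjects with an event.

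| Assumed loss | Margin 0.20: recorded rates, placebo / FMT | Wald | Score | Margin 0.25: recorded rates, placebo / FMT | Wald | Score |
|---|---|---|---|---|---|---|
| None | 0.10 / 0.30 | 0.0540 | 0.0380 | 0.15 / 0.40 | 0.0488 | 0.0488 |
| 5 points, placebo only | 0.05 / 0.30 | 0.0225 | 0.0143 | 0.10 / 0.40 | 0.0180 | 0.0180 |
| 5 points, each arm | 0.05 / 0.25 | 0.0721 | 0.0483 | 0.10 / 0.35 | 0.0524 | 0.0521 |
| 5 points, FMT only | 0.10 / 0.25 | 0.1355 | 0.0993 | 0.15 / 0.35 | 0.1152 | 0.1151 |
| One quarter, both arms | 0.075 / 0.225 | 0.1613 | 0.1185 | 0.1125 / 0.30 | 0.1531 | 0.1525 |

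Five points is not the same share of events in each arm: at margin 0.20 it is half of placebo events (0.05/0.10) and one sixth of FMT events (0.05/0.30). The error rate can fall or rise. An equal proportional loss shrinks the observed difference and roughly triples the Wald error at margin 0.20 (0.1613/0.0540 = 3.0).

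**The case against.** The strongest reply is that the 6.1 sentence only echoes the wording of the one before it, whose subject is expedited DSMB reporting, so it was meant to limit that reporting alone. The opening of 6.1, the AE assessments at every treatment visit (sections 5.1 and 5.2.2) and the section 8 log all fit that reading, and on it no event is lost. This may well be the intent. But it requires the reader to ignore the verb *recorded*, and no section says which rule prevails. The loss is therefore conditional, while the conflict in the text is not.

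A second reply is that the 6.1 criteria cannot be applied unless a blinded investigator has already judged grade, expectedness and relationship, so those judgements must exist. That is fair. What remains unstated is whether they are kept for events that are not reported.

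A third is that the loss fractions in the calculation are invented, and that classification by a blinded investigator makes a one-arm loss hard to justify. This stands as a limit: the figures show that the direction is open and that the effect need not be small, and nothing more. Part of the 7.1 rate is also protected, because SAEs are kept unless the lead-in governs the whole list.

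Finally, the missing baseline grade would exist even without the sentence. That is true, but deleting the sentence would still leave 7.3 without a reference for an upgrade, so it belongs in the same correction.

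**Conclusion.** The point holds: the recording rule in 6.1 is wrong as written and should be corrected. Taken literally, it excludes expected FMT-related grade 2 events from a primary outcome that counts them. It also excludes some worsening events from the primary comparison, and it conflicts with section 8.

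For 5.3.3 the direction is known: the observed proportion can only fall or stay the same. For the 7.3 equivalence test neither size nor direction can be stated, because the documents give no capture rate, no definition of expectedness and no variance method. Across the assumed losses, the chance of wrongly declaring equivalence at margin 0.20 runs from 2.3% to 16.1% (Wald) or 1.4% to 11.9% (score), against 5.4% and 3.8% with full capture. Confidence is high on the wording conflict; the consequence depends on how the site applies the sentence.

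**What to change.** 1. In 6.1, state that the listed criteria govern expedited DSMB reporting only, and remove the reference to recording from the restrictive sentence.
2. State whether *unexpected* applies to the SAE and grade 3 items or only to the grade 2 item.
3. State that all AEs in both arms are entered on the case report form with CTCAE grade, dates, seriousness, expectedness and relatedness. Name one start point for this, reconciled with the period after enrolment in 7.1 and with the 7.3 analysis set.
4. Grade existing symptoms at the Day -8 AE assessment, so that worsening or upgrade has a reference.
5. Make section 8 refer to the same rule.

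The cost is protocol wording, more AE lines in the database, and a baseline grade entry for each existing symptom. AE assessment is already scheduled at Day -8 and at each treatment visit, so no visit or procedure is added. The difference between the 5.3.3 outcome and the 7.1/7.3 endpoint is a separate matter that this change does not settle.

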6.2. Safety and Data Monitoring

A data and safety monitoring board consisting of three physicians and a biostatistician independent of the principal investigator will monitor this study. The DSMB will review all adverse events as previously described and will convene at least every four months or when needed to review initial limited cohort safety data as described previously. Additionally, the DSMB will be convened to evaluate subject data if the subject has been temporarily halted from participating in the trial in order to assess appropriateness of resuming participation in the trial.

If an SAE is thought to have been caused by the fecal transfer, the DSMB and IRB recommendation as to whether the protocol should be suspended or not will be followed.

6.3. Clinical Monitoring

Monitoring will be conducted according to a written monitoring plan to ensure the protection of the rights and safety of all participating human subjects, as well as to ensure the quality and integrity of data resulting from this investigation. Monitoring services will be performed by qualified monitors provided by Boston Children's Hospital.

7. STATISTICAL CONSIDERATIONS

7.1. Power Calculation

The primary aim of this phase I/II study is to establish whether or not FMT is a safe treatment for children and young adults with UC. Based on clinical experience, adverse events (AEs) in IBD patients are common and include abdominal pain, cramping, diarrhea, fever, bloody stool, vomiting, frequent defecation, joint pain, and eye pain. It's estimated that 70% of patients in any given year will experience a flare of their disease and have some or a combination of these symptoms. Safety, therefore, needs to be assessed relative to the high prevalence of AEs in this population. For the primary outcome, we will take any new reported SAEs or worsening of the existing AEs during the study period following enrollment into account.

The study will be powered for equivalence in the proportion of new SAEs or worsening of the existing AEs, assuming null (Ho) and alternative (Ha) hypotheses defined as follows:

$$\begin{split} & \text{Ho: } p1-p2 \leq \text{-}\delta_L \ \text{ or } p1-p2 \geq \delta_U. \\ & \text{Ha: } \delta_L \leq p1-p2 \leq \delta_U \end{split}$$

where p1 is the proportion of new SAEs or worsening of the existing AEs in the placebo group, p2 is the proportion in the FMT group, δ_L is the lower margin and δ_U is the upper margin. We expect to enroll a total of 60 patients into this study for a total of 30 FMT and 30 placebo patients. Assuming the rate of new incident SAEs or worsening of existing AEs in the placebo group is 10%, there will be 82% power to reject Ho that the difference in proportions is 0.20 or greater from zero in the same direction. Similarly, we will have an 85% power to reject a difference of 0.25 or greater if the rate of new incident SAEs or worsening of existing AEs increases to 15%.

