4.1.4. Blinding and Randomization

The first ten eligible subjects will be randomized in a 1:1 ratio according to a pre-determined block randomization procedure to receive either FMT or placebo. If safety allows, the remaining cohort of 50 eligible subjects will be randomized in a 1:1 ratio according to a pre-determined block randomization procedure to receive either FMT or placebo. An unblinded pharmacist or delegate will maintain the randomization list ensuring subjects are randomized appropriately and dispensed the correct treatment. The investigator, research personnel and study subjects will be blinded to treatment assignments.

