7.2. Simon's two stage design

We will follow stopping rule in Simon's two-stage design if high incidence of new SAEs occurred in study participants. In the first stage, a subset of 5 patients will be enrolled. If all the 5 patients develop new SAE in the study period, we will declare the study is not safe for patients and will stop the trial immediately to check if FMT is related to these SAEs. If less than 5 patients develop SAEs in the first stage, we will proceed to second stage to enroll another 5 patients. If 7 out of the total 10 patients enrolled develop at least one SAE, we will stop again and check if FMT is related to these SAEs. Otherwise the enrollment will be continued until the sample size for the primary outcome analysis is met.

Assuming the probability of the new SAE is 76% among study participants, following the 5/5 and 7/10 two-stage stopping rule, we will have 25% chance to stop in the first stage, and 80% chance to stop in the second stage. If probability of new SAE increases to 0.96, we will have 82% chance to stop in the first stage, and 100% chance to stop in the second stage.

True probability of SAE	0.76	0.80	0.90	0.96	0.98
Probability to stop in the first stage	0.25	0.33	0.59	0.82	0.90
Probability to stop in the second stage	0.80	0.88	0.99	1.00	1.00

Table. The probability of stop following 5/5 and 7/10 stopping rule in two-stage design.

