7.3. Data Analysis

All patients who are eligible, randomized, and have received at least one-dose of the study medication including antibiotics/placebo in the first week will be included into the analysis for primary outcomes to assess the safety and tolerability of FMT, as this will be a per protocol (and not intent-to-treat) analysis . Continuous variables will be presented as mean and standard deviation (SD) or median and interquartile range (IQR), depending on the distribution of the data. Categorical variables will be presented as number and percentage. Disease severity (PUCAI) and patient characteristics at baseline will be compared between the treatment groups to determine whether or not randomization resulted in balanced groups. Methods of 2-group comparison will include Student's t-test, the Mann-Whitney test, Pearson chi-square test, and Fisher exact test, depending on the distribution of the variable under consideration. The primary outcome of safety will be assessed via a 2×2 cross-tabulation, where the proportion of patients with new incident SAEs or upgrade of existing AEs in the FMT group will be compared to the proportion in the placebo group. Two one-sided tests for equivalence (32) will be constructed and the overall *P* value taken to be the larger of the lower and upper tests. Statistical significance will be assessed at *P*<0.05.

For the second outcome, we will use longitudinal data analysis methods to investigate changes in inflammatory biomarkers including stool calprotectin, stool lactoferrin, serum ESR/CRP, albumin, and hematocrit over the study period. Generalized Estimating Equations will be performed to examine the association between FMT and changes in these biomarkers.

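### The 82% and 85% power in section 7.1 belong to a single one-sided test; the planned equivalence analysis (two one-sided tests) has about 65% and 71% at the plan's own inputs

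*Combined protocol and SAP*

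**What the plan says.** Section 7.1 (Power Calculation) sets up a two-sided equivalence null: the difference between arms lies beyond a lower or an upper margin. The event is a new serious adverse event or a worsening of an adverse event already present. The sample is "a total of 30 FMT and 30 placebo patients", and section 4.1.4 has subjects "randomized in a 1:1 ratio".

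Two power statements follow. With a placebo rate of 10% and a difference of 0.20, "there will be 82% power to reject Ho". If the rate is 15%, power is given as 85%, but for a difference of 0.25. No source is given for either rate, and the assumed true difference is not stated.

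Just before this, the same section says adverse events are common in this population and that "70% of patients in any given year will experience a flare of their disease". It does not connect that figure to the 10% or 15%. The window for the event is the study period, with no length given. Section 5.3.3 words the primary outcome differently and places it at 8 weeks. Sections 3.1 and 5.2.3 end the blinded comparison at 8 weeks.

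Section 7.3 (Data Analysis) says "Two one-sided tests for equivalence (32) will be constructed", takes the larger of the two P values as the overall one, and adds "Statistical significance will be assessed at *P*<0.05".

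**The concern.** Equivalence is shown only if both one-sided tests reject. When the true difference is zero, each test can fail by chance, so the power of the pair is lower than the power of either test alone. Section 7.1 describes the pair but appears to report the power of one.

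The second scenario adds to the problem. A higher event rate means a larger variance and less power at a fixed margin. Here the margin is widened at the same time, so power seems to rise from 82% to 85% as the rate goes up. A reader cannot see what a rate above 10% does at margin 0.20.

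This matters for how the result is read. If FMT carries no excess risk, the plan implies an 18% or 15% chance of failing to show equivalence. The actual chance under its own analysis is about 35% or 29%. In a trial whose primary aim is safety, such a failure could be taken as a safety signal when it reflects limited power.

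**Working it through.** **Inputs**
- n = 30 per arm, 1:1 (sections 7.1 and 4.1.4).
- Each one-sided test at 0.05, z = 1.645 (section 7.3).
- Rate p and margin m: 10% with 0.20, and 15% with 0.25 (section 7.1).
- True difference 0 and no dropout: assumptions, since section 7.1 states neither.

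**Formulas** (normal approximation, unpooled variance)
- SE = sqrt(2p(1−p)/n)
- One one-sided test: Φ(m/SE − 1.645)
- TOST: 2Φ(m/SE − 1.645) − 1, or 0 if this is negative

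**Step 1. Reproduce the stated figures.**
- p = 0.10, m = 0.20: SE = sqrt(0.18/30) = 0.0775; 0.20/0.0775 = 2.582; 2.582 − 1.645 = 0.937; Φ = 0.826. Stated: 82%.
- p = 0.15, m = 0.25: SE = sqrt(0.255/30) = 0.0922; 0.25/0.0922 = 2.712; 2.712 − 1.645 = 1.067; Φ = 0.857. Stated: 85%.

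Both match a single one-sided 0.05 test. A one-sided 0.025 test gives 73.3% and 77.4%, and a continuity correction gives 69.4% and 76.0%. Neither variant matches.

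**Step 2. Power of the planned analysis at the same inputs.**
- 2 × 0.8257 − 1 = 0.651.
- 2 × 0.8570 − 1 = 0.714.

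Enumerating all binomial outcomes for the Wald version of TOST gives 67.4% and 69.5%, so the shortfall does not come from the normal approximation.

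**Step 3. Put the yearly flare figure on the 8-week scale** (the conversion is an assumption).
- Pro rata: 0.70 × 8/52 = 10.8%.
- Constant hazard: 1 − 0.30^(8/52) = 16.9%.

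**Step 4. Hold the margin fixed and vary the rate** (n = 30 per arm, true difference 0, normal approximation).

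| Placebo rate | TOST, margin 0.20 | TOST, margin 0.25 | Single one-sided, margin 0.20 | Single one-sided, margin 0.25 |
|---|---|---|---|---|
| 10% | 65% | 89% | 83% | 94% |
| 10.8% | 61% | 86% | 80% | 93% |
| 15% | 40% | 71% | 70% | 86% |
| 16.9% | 33% | 65% | 66% | 83% |
| 20% | 23% | 56% | 61% | 78% |
| 25% | 11% | 45% | 56% | 72% |
| 30% | 4% | 36% | 52% | 68% |
| 40% | 0% | 26% | 47% | 63% |

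Exact Wald enumeration at margin 0.20 gives slightly higher TOST values (44% at 15%, 37% at 16.9%, 15% at 25%) and the same pattern.

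**The case against.** The strongest defence is that the stated figures are correct for what was calculated. Section 7.1 speaks of rejecting a difference in the same direction, and for a safety question the direction of interest is harm from FMT. On that one-sided reading, 82% and 85% stand. But section 7.1 calls the study powered for equivalence and writes a null with two margins, and section 7.3 requires both tests to succeed. The power quoted has to be that of the analysis planned.

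It is also fair to say that most of the shortfall at the plan's own inputs comes from the test and not from the event rate. At margin 0.25, moving from 15% to 16.9% lowers TOST power only from 71% to 65%.

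A reader might infer more than the documents support:

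- **That the 70% flare figure contradicts 10-15%.** It is a 12-month rate of any flare. Over 8 weeks it becomes about 11% to 17%, which overlaps or sits just above the assumed range. A flare is also not the primary event: subjects enter with active disease, and symptoms already present count only if they worsen.
- **That 34 weeks (8 weeks plus 6 months) is the relevant window.** The undefined study period leaves room for this. However, section 5.2.3 unblinds subjects after week 8 and lets placebo subjects who did not improve take open-label FMT, so a later comparison would no longer be a clean randomized one.
- **That section 7.2 contradicts section 7.1.** "Assuming the probability of the new SAE is 76% among study participants" introduces the lowest of five hypothetical rates (0.76 to 0.98) used to show how often a stopping rule would trigger. It is not a forecast, and the two sections need not share one set of rates.
- **That TOST power at margin 0.20 is zero at every rate above about 33%.** In the normal approximation it is zero between about 33% and 67%, because the variance peaks at 50%. It then returns, for example to 4% at 70% and 13% at 76%.

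**Conclusion.** The stated power is not the power of the planned analysis. At the plan's own rates and margins, TOST power with 30 per arm is about 65% instead of 82%, and about 71% instead of 85%: shortfalls of about 17 and 14 percentage points. This rests on a true difference of zero, the most favourable case for equivalence with symmetric margins at a given placebo rate and variance, and on no dropout. It needs no view on the flare rate.

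Power also depends strongly on the assumed rate, and widening the margin between scenarios conceals this. At margin 0.20, TOST power is 40% at 15%, about 33% at 17% and 11% at 25%. The 17% relies on the constant-hazard conversion; pro rata conversion gives 10.8% and about 61%. The 10-15% rate is unsourced and not tied to a window, but the documents do not show it to be wrong.

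**What to change.** In section 7.1:

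1. Replace 82% and 85% with the TOST figures (about 65% and 71%). State the method, the 0.05 level for each one-sided test and the assumed true difference.
2. Choose one margin and give a table of TOST power for 30 per arm over placebo rates of 10% to 40%, as in the working above.
3. Tie the assumed rate to the 8-week blinded window, give its basis, and show how it relates to the 70% yearly flare figure.

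The cost is revised wording, one table and a less favourable stated power. No patients need to be added. For information only, keeping the stated power under TOST at the same rates and margins would take about 41 per arm for 82% and 39 per arm for 85%, from n = 2p(1−p)(1.645 + z)²/m², where z is the normal quantile at (1 + power)/2.
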